## **1. Introduction and Purpose:**

Sepsis is the leading cause of neonatal mortality and every year three million infants die worldwide due to neonatal sepsis (1). In the US, despite significant advances in care, sepsis remains a significant cause of neonatal morbidity and mortality, particularly among Very Low Birthweight (VLBW) preterm infants (PI) (2).

Neonatal early onset sepsis (EOS) is defined as onset of signs and symptoms of sepsis with positive culture <72 hours of age. Compared to term infants, the incidence of EOS is 11 times higher in preterm infants with a mortality rate ranging from 1.5% in term infants to almost 40% in VLBW preterm infants (2).

The diagnosis of neonatal sepsis is challenging, and the prognosis depends on early detection and treatment. The current “gold standard” to diagnose sepsis is a positive blood culture, but there is a variable sensitivity mostly due to inadequate sample volume, transient bacteremia, intrapartum antibiotics and administration of antibiotics before blood sample collection (3,4,5). Although the gold standard for diagnosis of bacterial sepsis is blood culture, only in 25%-40% of blood culture pathogens can be detected (6). Serum markers as IL-6 and CRP have shown to be suitable markers for detecting early onset neonatal sepsis, with a high degree of sensitivity and specificity (18).

In VLBW infants, almost 3 ml of blood is drawn to evaluate EOS for blood culture, CBC and blood group and cross match. This baseline work-up laboratory may represent almost 5-10% total blood volume of a VLBW infant. This iatrogenic acute blood loss may lead to hemodynamic instability and early red blood transfusion in the preterm infant when they are at the highest period risk for intra ventricular hemorrhage (IVH) (23).

The average infant's blood volume is 80ml/kg, while the average blood in the placenta and umbilical cord is 15 to 34 ml/kg which is discarded in the current practice (29). EOS evaluation which includes blood culture, CBC, IT ratio along with biomarkers of EOS like CRP and IL-6 could be done by using placenta/umbilical cord blood (PUCB). PUCB collection is painless, easy and adequate volume may be collected for blood culture. This procedure could decrease iatrogenic blood losses of VLBW infants (23). Currently, there is inadequate published data to support the routine use of PUCB in the evaluation of EOS in VLBW preterm infants.

The purpose of the present study is to evaluate the utility of placenta/umbilical cord blood (PUCB) to perform the baseline workup testing (CBC, I/T ratio, blood culture) along with CRP and IL-6 levels in the evaluation of EOS in VLBW infants.

## **2. Background:**

Early and timely diagnosis of EOS is very important but challenging at the same time as clinical signs are nonspecific. Routine Laboratory tests such as complete white blood count (WBC) with differential count and immature/total neutrophil (I/T) ratio are routinely used to assist in the diagnosis of sepsis in neonates; however, multiple studies have determined that the WBC and immature-to-total neutrophil (I/T) ratio have low sensitivities and specificities (7). The I/T ratio has been found elevated in a quarter to half of the presumptively in infants without sepsis (8,9) with low positive predictive values (7). Consequently, just CBC indices in the evaluation of EOS in neonates is not very helpful, hence use of empiric antibiotic therapy is used in a large number of neonates with clinical suspicion of EOS (8,9).

The “Gold Standard,” blood cultures are not always positive because of low blood volumes are often put in the blood culture bottles and prenatal administration of antibiotics (6, 27). Using biomarkers of sepsis to distinguish septic from non-septic neonates may allow judicious discontinuation of antibiotics, consequently preventing prolonged use of antibiotics and avoiding the appearance of antibiotic-resistant bacteria. Besides, appearance of antibiotic-resistant bacteria, prolonged empiric antibiotic use has been associated with increased risk of necrotizing enterocolitis (NEC), late onset sepsis (LOS), and even increased mortality (10).

Recent studies have shown improved sensitivity and negative predictive value (NPV) of various biomarkers of sepsis compared to CBC indices (11,12). Acute phase proteins, components of the complement system, chemokines, cytokines, adhesion molecules, and cell surface markers have all been investigated as biomarkers of neonatal sepsis (12). The most widely studied and most promising markers include C-reactive protein (CRP), interleukin-6 (IL-6), interleukin-8 (IL-8), procalcitonin (PCT), and tumor-necrosis-factor-alpha (TNF-alpha).

## 2.1 *C-Reactive Protein (CRP)*

CRP is one of the most sensitive acute-phase reactants for inflammation. CRP is synthesized by the liver. The CRP response frequently precedes clinical symptoms of sepsis. CRP acts within the humoral immune system, particularly in the detection and clearance of bacterial microorganisms. CRP level increases within 6-18 hours after a stimulus and peaks 8-60 hours later (13). The fetus and newborn synthesize CRP; its level is not affected by gestational age, and CRP does not cross the trans-placental passage of maternal CRP (14).

CRP elevations are nonspecific and may be useful for the detection of systemic inflammatory processes; to assess treatment of bacterial infections with antibiotics. In neonates, CRP has been shown to be more sensitive and specific in diagnosing sepsis than the more commonly used CBC indices (total neutrophil count and I/T ratio) (15). Joram et al found that CRP (cut-off point of 5 mg/dl) measured in umbilical cord blood has a sensitivity, specificity, positive and negative predictive values are respectively 50%, 97%, 67% and 94%. Besides, the same study found that the positive and negative likelihood ratios were 16.7 and 0.5 for CRP (28).

## 2.2 *IL-6*

IL-6 is a pro-inflammatory cytokine produced by mononuclear phagocytes, endothelial cells, and fibroblasts in response to inflammation. IL-6 levels peaks 2-3 hours after inflammatory

responses, and returns to baseline after 6 to 8 hours (16). IL-6 is the primary inducer of hepatic acute-phase protein synthesis, including CRP and fibrinogen (17). IL-6 levels are not influenced by gestational age and has been shown to have high sensitivity in diagnosing EOS (16,18).

Messer et al. in a prospective study, measured IL-6 levels (n=157) upon admission to the NICU and the in umbilical cord blood (n=131) (18). The sensitivity and NPV of IL-6 in the diagnosis of blood culture positive and clinical sepsis was 100% in those infants who had an early measurement of IL-6 at birth (umbilical cord blood) or blood drawn from the infant within one hour after birth. Moreover, they found high sensitivity and NPV persisted until the twelfth hour of age. Krueger et al. found umbilical cord blood IL-6 levels have high sensitivity (87%) and specificity (90%) in 71 term and 100 preterm infants. When only preterm infants were included in the analysis, IL-6 sensitivity and specificity increased to 96% and 94% (19).

### *2.3 Combination of Biomarkers*

Because single biomarker cannot be reliably used to diagnose EOS, many investigators have used combinations of biomarkers to improve the sensitivity and specificity in diagnosing EOS. Buck et al. (20) found the sensitivity of IL-6 in CRP-negative newborns and the sensitivity of CRP in IL-6 negative newborns on admission to be 100% in newborns with blood-culture positive or clinical sepsis. They concluded that the combination of IL-6 and CRP is the best combination of biomarkers of sepsis in diagnosis of EOS. Doellner et al. (21) also found the combination of IL-6 and CRP is superior in diagnosing neonatal sepsis than either parameter alone. Laborada et al. also concluded that the combination of IL-6 and CRP is the best diagnostic test for the detection of EOS sepsis in preterm infants (22).

### *2.4 Reducing blood withdrawals in preterm infants*

Placental/umbilical cord blood (PUCB) could be used in the evaluation of EOS in PI. (23,26). Christensen found reduced iatrogenic blood loss using PUCB sample during the first day of life ( $p < 0.007$ ), and for the first week of life ( $p < 0.001$ ) in contrast with infant blood sample controls (23). This postpone or eliminating blood transfusion in the VLBW preterm infant (23,26).

PUCB for blood cultures could be a convenient alternative to ensure an adequate volume of blood (24). Meena et al. compared PUCB with blood from infants, (n=40) in the evaluation of sepsis. They found PUCB showed 100% sensitivity and 95% of specificity compared with 100% of sensitivity and 74% of specificity using blood from infants. Beeram et al found that the utilization of umbilical blood samples for CBC and blood cultures are a reliable alternative for sepsis workup in neonates (25).

In the current study, we want to find out the efficacy of PUCB in the evaluation of EOS in preterm infants compared to blood collected from the infant (24).

## **3. Concise Summary of Project:**

Hypothesis: Placental/umbilical cord blood can be used to do early onset sepsis evaluation in low birth weight infants.

Objective: To compare placental/umbilical cord blood and blood from the infant in the evaluation of EOS in VLBW infants.

Specific Aim 1: To compare blood culture, CBC and I/T ratio results of blood from the infant and placental/umbilical cord blood (PUCB).

Objective: All VLBW infants receive empirical broad-spectrum antibiotics after collecting blood for CBC, I/T ratio, and blood culture. We will compare the results of PUCB and blood from the infants, especially comparing white cell count, band count, I/T ratio and if the blood culture is positive or negative. If the blood culture is positive, then we will find out if the micro-organism is the same or not.

Specific Aim 2: To evaluate the role of adding IL-6 and CRP in the evaluation of EOS in VLBW infants.

Objective: We will collect 1 mL of PUCB which will be centrifuged at -40C and serum will be stored at -80 degrees. We will use ELISA to measure IL-6 and CRP. A combination of IL-6 and CRP has been shown to be very helpful in the diagnosis of EOS in VLBW infants. We will also calculate sensitivity, specificity, negative predictive and positive predictive values of IL-6 and CRP individually, as well as, a combination of IL-6 and CRP in the diagnosis of EOS in VLBW infants. We will also find out the duration of antibiotics used in all subjects and find out from IL-6 and CRP data if the antibiotic use was warranted. In future, this may be very useful information in deciding antibiotic duration which will help in avoiding side effects of the unnecessary use of broad-spectrum antibiotics. At present, in our NICU, IL-6 and CRP are not part of EOS evaluation in VLBW infants.

Clinical team will be blinded to the PUCB sepsis evaluation results. In the present study, IL-6 and CRP will not be used clinically but only for research purpose to find out if the addition of IL-6 and CRP help in the management of EOS in VLBW infants.

All VLBW infants get CBC done at admission before starting antibiotics as part of EOS work up. After CBC is done, left over blood sample is saved in the hematology laboratory for 24 hours. We will collect the left-over sample and collect serum after centrifugation. The serum will be saved at -800C for future measurement of IL-6 and CRP. We will compare IL-6 and CRP from infant and PUCB.

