#### *Routine management of VLBW infants in NICU at UTMB Galveston:*

In NICU at UTMB Galveston, routinely, all VLBW infants admitted to NICU get sepsis evaluation by collecting blood from infant for CBC, I/T ratio, and blood culture followed by a course of empiric antibiotics for 2 – 3 days. This requires almost 2 – 3 mL of blood volume which may be up to 5% blood loss in an extremely premature infant which may lead to hemodynamic instability and anemia, resulting in the requirement for blood transfusion. If the sepsis evaluation is not conclusive, then the course of antibiotics may be extended to 3 to 7 days. Addition of CRP and IL-6 in EOS evaluation may be helpful in determining the duration of antibiotics. However, in NICU at UTMB Galveston, CRP and IL-6 are not part of EOS evaluation.

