#### *Placenta/Umbilical Cord blood (PUCB):*

In the current research project, we want to use PUCB to do sepsis evaluation in VLBW infants. There is approximately 15 – 20 mL/kg blood in the placenta and umbilical cord. That means in VLBW infants (<34 w) there will be approximately 15 – 20 mL blood in the placenta and umbilical cord which is fetal blood hence it can be utilized to do EOS sepsis evaluation. This

will save blood in VLBW infants. As blood in PUCB is nothing but fetal blood. There is a misconception that fetal and maternal blood is mixed in the placenta. Actually, there is no mixing of maternal and fetal blood in the placenta. After birth, the placenta and umbilical cord are discarded along with the blood inside. We want to utilize fetal blood in the placenta/umbilical cord for the evaluation of EOS in VLBW infants.

The current research project will evaluate the utility of PUCB to assess early onset sepsis (EOS) in VLBW infants (<34 weeks). This study will not affect the management of the infants at all. The lab tests will be done in blocks and hence the results will not be available in real time. The clinical management of infants will be decided by the neonatal team taking care of the infants. The neonatologists will continue to treat infants as per the NICU protocol.

We will compare blood culture, CBC, and I/T ratio results from the infant and PUCB. We will calculate the sensitivity, specificity, positive and negative predictive value of these tests in the evaluation of EOS.

During hospital stay, all VLBW infants get CBC done immediately after birth. After CBC is done, the left-over sample is stored in the hematology laboratory for 24 hours. After 24 hours, this blood sample is discarded. We will collect left over blood from the hematology laboratory to extract serum by centrifuging the blood sample. The serum will be stored at -80°C for future measurements of CRP and IL-6. We will also compare CRP and IL-6 levels in placenta/umbilical cord blood and discarded infant blood. Additionally, we will evaluate the role of adding IL-6 and CRP in the evaluation of EOS in VLBW infants.

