## **6. Criteria for Inclusion of Subjects:**

**Inclusion criteria:** Subjects who will fulfil following criteria will be included in the study -

1. Infants < 34 weeks' gestational age, born at UTMB, Galveston

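### With few positive infant cultures to be expected among 63 infants, the planned culture comparison can look favourable while barely testing whether cord culture detects infection

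*Combined protocol and SAP*

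**What the plan says.** The hypothesis in section 3 is broad: "Placental/umbilical cord blood can be used to do early onset sepsis evaluation in low birth weight infants". For culture, Specific Aim 1 plans two comparisons of cord and infant blood. The first is of results, "especially comparing white cell count, band count, I/T ratio and if the blood culture is positive or negative". The second is conditional: "If the blood culture is positive, then we will find out if the micro-organism is the same or not".

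The later part of section 3 on placenta/umbilical cord blood (PUCB) adds accuracy measures for blood culture, CBC and I/T ratio: "We will calculate the sensitivity, specificity, positive and negative predictive value of these tests in the evaluation of EOS". The Clinical Data Collection part of section 3 repeats this and names blood culture.

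Entry is by gestation and birthplace only (section 6): "Infants < 34 weeks' gestational age, born at UTMB, Galveston". Infant culture is not triggered by suspicion of sepsis: "routinely, all VLBW infants admitted to NICU get sepsis evaluation by collecting blood from infant for CBC, I/T ratio, and blood culture". Section 1 defines EOS as "onset of signs and symptoms of sepsis with positive culture <72 hours of age". The only incidence statement there is relative to term infants: "the incidence of EOS is 11 times higher in preterm infants".

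The target of 63 comes from a correlation of CRP with other biomarkers (section 3, Power analysis). Section 14 assigns categorical variables to a linear-by-linear chi-squared test. It names no confidence interval, paired test, agreement measure or expected number of positive cultures.

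**The concern.** Pairs in which both cultures are negative carry no information on whether cord culture finds a pathogen that is present. If positive infant cultures are few, such pairs make up nearly the whole comparison. Specificity, negative predictive value, overall agreement and a non-significant test can then all look reassuring while detection has been tried in no infant or in a handful. The organism comparison may have no infant to apply to.

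What is at stake is the culture part of the hypothesis. The error that matters most for that claim is an infection that the infant's culture shows and the cord culture misses. These summaries respond least to that error.

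**Working it through.** **The plan's own figure.** Section 3 gives r = 0.4, alpha 0.05, power 0.95 and n = 63. By Fisher's z, n = ((z_alpha + z_power)/atanh r)² + 3. One-sided, this is ((1.645 + 1.645)/0.4236)² + 3 = 63.3; a bias-corrected version gives 63 (power 0.952). The figure therefore reproduces as a one-sided test. A two-sided test, as section 14 specifies, needs 75 to 76, which is a separate matter. What counts here is that no culture quantity enters the calculation.

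**Inputs.**
- n = 63 pairs (section 3). This assumes that every enrolled infant has both cultures.
- Infant-culture positivity p is not in the documents. Assumed: 1%, 2% and 5%.
- Stress case of 11%, derived from the cord-blood CRP study cited in section 2.1 (sensitivity 50%, specificity 97%, PPV 67%). Solving PPV = 0.50p/(0.50p + 0.03(1 − p)) = 0.67 gives p = 0.0201/(0.165 + 0.0201) = 10.9%. This returns NPV = 94%, as cited. The documents do not say that those cases were culture-positive, so 11% is only a proxy.

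**Step 1: how many positives.** Expected number = 63p; chance of none = (1 − p)^63; chance of three or fewer from the binomial(63, p).

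**Step 2: a cord culture that never grows anything.** Expected overall agreement and negative predictive value are both 1 − p. Specificity is 100%.

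| Assumed p | Expected positives | Chance of none | Chance of 3 or fewer | Agreement and NPV |
|---|---|---|---|---|
| 1% | 0.6 | 53% | 99.6% | 99% |
| 2% | 1.3 | 28% | 96% | 98% |
| 5% | 3.2 | 4% | 61% | 95% |
| 11% | 6.9 | 0.1% | 7% | 89% |

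**Step 3: the named test.** Take x infant positives and no cord positives, with the two sets of 63 results treated as two samples. The linear-by-linear statistic is x(2n − 1)/(2n − x) = 125x/(126 − x), on 1 degree of freedom.

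| x | Statistic | p | Exact McNemar p | Observed agreement | Upper 95% limit for sensitivity 0/x |
|---|---|---|---|---|---|
| 1 | 1.00 | 0.32 | 1.0 | 98.4% | 97.5% |
| 2 | 2.02 | 0.16 | 0.5 | 96.8% | 84% |
| 3 | 3.05 | 0.08 | 0.25 | 95.2% | 71% |

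A complete failure of detection is thus non-significant with up to three positives. Moving to a paired test does not cure this. With four positives the chi-squared p falls to 0.043. If the test were instead run on the cord-by-infant cross-table, it would be undefined, because the cord result would not vary.

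**Step 4: what can be estimated.** When all x positives are matched, the exact lower 95% limit for detection is 0.025^(1/x): 16% for 2/2 and 48% for 5/5. Excess cord growth is much better determined: 0/60 has an exact upper limit of 1 − 0.025^(1/60) = 6%, and 3/60 has one of 14%.

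**The case against.** The strongest reply is that sensitivity is already planned. If even one infant culture is positive, a cord culture that never grows anything has 0% sensitivity, which nobody would call good agreement. This stands, and it rules out the claim that the plan as a whole would return a near-perfect result. It is a thin safeguard, though. At 1% or 2% positivity, sensitivity is undefined with probability 53% or 28%; otherwise it usually rests on one to three infants, with no interval to show how little is known.

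Four further points stand in part.
- The documents never name overall agreement as the statistic or as a criterion of success. A reader might infer that they do, but Aim 1 says only that results will be compared. The agreement figures above show how one natural summary would behave.
- The size depends on an assumed positivity, and at 11% it shrinks.
- Cord contamination would lower agreement. At the 95% cord-culture specificity cited in section 2.4 and 2% positivity, agreement would be 0.98 × 0.95 = 93%, with about 3 pairs (63 × 0.98 × 0.05) discordant through excess growth. That measures false positives and still says nothing about detection.
- A reader might infer that the cohort ought to be enriched for infants at risk. The documents do not support that: the unit evaluates all VLBW admissions routinely, so unselected entry matches the intended use, and selection by risk would distort the predictive values.

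**Conclusion.** The point holds as one about analysis and reporting. At an assumed 1% to 5% positivity, 63 infants give 0.6 to 3.2 expected positive infant cultures. A cord culture with no ability to detect infection would still show 95% to 99% expected agreement and negative predictive value, and the only categorical test named would miss the failure with three or fewer positives. The chance of three or fewer is 99.6%, 96% and 61% at 1%, 2% and 5%. At 11% a failure would probably show.

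This rests on the assumed positivity, on both cultures being available for all 63 infants, and, for the agreement and specificity figures, on no cord contamination.

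A reader might go further and infer that the study will endorse replacing the infant draw. The documents do not say so. Section 3 states that infants' management is unaffected, and section 13 says only that the results may help to show whether cord blood could be used. The gap is that nothing in the plan limits the culture conclusion to what the positives can support.

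**What to change.** Amend Specific Aim 1 and the PUCB part of section 3, and section 14, as follows.

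1. State that a non-significant chi-squared test, the negative predictive value and overall agreement will not be used as evidence that cord culture detects infection.
2. Report two results, with infant culture as the stated reference:
   - detection: among infants with a positive infant culture, the number with the same organism in PUCB, with an exact 95% interval;
   - excess growth: among infants with a negative infant culture, the proportion with any PUCB growth, with an exact 95% interval.
3. State in advance that any conclusion on the ability of cord culture to detect infection is limited by the lower limit of the detection interval, and that with no positive infant culture no conclusion on detection is drawn.

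A fixed minimum number of positives is not needed. Any cut-off would be arbitrary (5/5 still leaves a lower limit of 48%), and the interval does the work.

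The cost is wording only: no extra infants, samples or tests, and the haematology comparison is untouched. The downside is that the culture conclusion will probably be narrower than the hypothesis.

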## **13. Potential Benefits:**

There will be no direct benefit to the subjects. But the results of this study may help us to find out if PUCB could be utilized to evaluate EOS in VLBW infants. The results of this study will provide understanding of the utility of PUBC samples to evaluate EOS in VLBW preterm infants. Moreover, this alternative modality of blood analysis could contribute to the prevention of early hemodynamic instability and early blood transfusion in a very high-risk population of VLBW preterm infants. Furthermore, an additional test for sepsis screening as CRP and IL 6, might improve the accuracy for EOS evaluation, and may avoid or prevent unnecessary and prolong antibiotic use in ELBW infants.

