## **14. Biostatistics:**

Statistical analyses will be performed using SPSS 25 for Windows (SPSS Inc., Chicago, IL, USA). Demographic and clinical characteristics will be compared using the non-parametric Mann-Whitney U test, and the results will be presented as medians (range). Categorical variables will be compared using the linear-by-linear association Chi-squared test and will be presented as percentages (%). Receiver operator curve (ROC) analysis will be employed to display the relationship between sensitivity and false positive (FP) rate (1-specificity) and to select the best cut-off value for umbilical cord IL-6 and CRP to predict EOS. Data will be as adjusted by gestational age at delivery, administration of prenatal corticosteroids and antibiotics. Differences will be considered statistically significant at a confidence level of  $p < 0.05$  with two-sided alternative hypotheses

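### Aim 2 asks what adding IL-6 and CRP contributes, but no planned analysis compares the current early tests with and without the markers in the same infant

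*Combined protocol and SAP*

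**What the plan says.** Section 3 states Specific Aim 2 as "To evaluate the role of adding IL-6 and CRP in the evaluation of EOS in VLBW infants", and the PUCB subsection of section 3 repeats it. Section 13 puts the expected benefit in the same terms: "an additional test for sepsis screening as CRP and IL 6, might improve the accuracy for EOS evaluation".

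The baseline is set out under routine management in section 3. It is "sepsis evaluation by collecting blood from infant for CBC, I/T ratio, and blood culture", and at this unit "CRP and IL-6 are not part of EOS evaluation".

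The outputs that bear on the aim are:
- Section 3, Aim 2: the four accuracy measures, described as "predictive values of IL-6 and CRP individually, as well as, a combination of IL-6 and CRP".
- Section 3, Aim 2: a look at antibiotic duration, to "find out from IL-6 and CRP data if the antibiotic use was warranted".
- Section 3, PUCB and Clinical Data Collection subsections: the same four measures for CBC, I/T ratio and blood culture; the second of these also lists CRP and IL-6.
- Section 3: marker levels in infant blood against cord blood.
- Section 14: ROC analysis "to select the best cut-off value for umbilical cord IL-6 and CRP to predict EOS", with adjustment for gestational age, prenatal steroids and antibiotics.

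**The concern.** Whether adding a test helps depends on how its results fall within the infants whom the existing tests have already classified. If IL-6 and CRP are positive in the same septic infants as the I/T ratio, each test can look accurate alone while the addition catches nobody new. If they are positive in different infants, the addition could be worth a good deal. Separate accuracy figures are compatible with both.

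The combination in the plan joins the two markers to each other, not to CBC or I/T ratio, and the section 14 adjustment does not include the current tests. A favourable IL-6/CRP result could therefore be read as support for adding the markers although the increment had not been measured. The protocol's own background uses the right kind of evidence: section 2.3 cites the sensitivity of one marker among newborns negative on the other. The plan has no counterpart for infants negative on CBC or I/T ratio.

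**Working it through.** **1. Is there a figure in the plan to reproduce?** There is none for a with-versus-without comparison. The only sizing is N = 63 for a correlation of r = 0.4, alpha 0.05, power 0.95 (section 3, Power analysis). By Fisher's z, one-sided: ((1.645 + 1.645)/0.4236)² + 3 = 63.3, so 63 reproduces. It serves here only as the ceiling on the number of infants.

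**2. Question against outputs.** Each output listed above describes one test, the two markers together, or agreement between specimens. None defines a rule or model that joins the markers to CBC or I/T ratio. None gives a change in sensitivity or specificity, a difference in AUC, nested models, or a paired count. The antibiotic review does set treatment given against marker results. It states no criterion and no comparator, and it takes the markers being evaluated as its own yardstick.

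**3. What separate figures leave open, infants without EOS.**

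Inputs:
- I/T ratio raised in 25% to 50% of infants without sepsis (section 2).
- IL-6 specificity of 94% in preterm infants, from a cited cord-blood study (section 2.2).
- Non-septic infants: assumed 60 of 63, because the documents give no EOS rate.

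Flagged alone:
- I/T ratio: 60 × 0.25 = 15, or 60 × 0.50 = 30.
- IL-6: 60 × (1 − 0.94) = 3.6, about 4.

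With a flagged by I/T and b by IL-6 among n infants, both-positive lies between max(0, a + b − n) and min(a, b). Either-positive is a + b minus both-positive.

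| I/T flags | IL-6 flags | Both positive | Either positive | Newly flagged (either rule) | Un-flagged (both rule) |
|---|---|---|---|---|---|
| 15 | 4 | 0–4 | 15–19 | 0–4 | 11–15 |
| 30 | 4 | 0–4 | 30–34 | 0–4 | 26–30 |

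The unknown overlap is worth 4 infants in each row. With 50 non-septic infants assumed instead, I/T flags about 13 or 25 and IL-6 flags 3; both-positive is 0–3 and either-positive is about 13–16 or 25–28. The illustration uses one early test and one marker only; CBC and CRP would alter the counts.

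**4. Infants with EOS.** If D infants have EOS, the early tests catch s and the markers catch m, the number newly caught lies between max(0, m − s) and min(m, D − s). The plan reports s and m for single tests but not this number.

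**5. Could the comparison be tested?** At assumed EOS rates of 2%, 5%, 10%, 20% and 30%, 63 infants give about 1.3, 3.2, 6.3, 12.6 and 18.9 cases. Under an either-positive rule sensitivity can only rise, so an exact two-sided McNemar test needs six newly caught cases (2 × 0.5⁶ = 0.031; five gives 0.0625). For 80% power, a 30-point gain needs 25 EOS cases. The study would not be expected to reach that at any of these rates.

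**6. Precision in infants without EOS.** Among 60, zero newly flagged has an exact 95% interval of 0 to 6.0%; 4 newly flagged has 1.8% to 16.2%.

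**The case against.** A reader might infer that the plan offers only stand-alone accuracy and leaves Aim 2 wholly unanswered. That goes too far. A combination of the two markers is planned, and the antibiotic review bears on the add-on role described under routine management. The defect is that the review lacks a criterion and comparator, not that nothing was planned.

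A reader might also take the whole span from 15 to 34 flagged infants as unresolvable. It is not. The planned I/T specificity would show whether the study is near 15 or near 30, which leaves only the overlap of about 4. Nor would the cost in extra false positives be hidden: under an either-positive rule, new false positives cannot exceed the marker's own, which the plan reports. And either-positive is not the protocol's rule. Section 2 presents the markers as an aid to stopping antibiotics, and routine management has every VLBW infant start them, so the flags correspond to no initial treatment decision.

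One could add that dropping culture makes the comparator artificial, since culture belongs to the work-up. That is true, but section 1 makes a positive culture part of the EOS definition, so a comparator that included it would be circular. Finally, EOS cases will be few. That limits what the comparison can show; it does not make separate figures a substitute for it.

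**Conclusion.** The point holds as a gap in the analysis plan. The aim and stated benefit are incremental, and the plan followed exactly would not measure the increment. In the illustration the gap among non-septic infants is modest: about 4 of an assumed 60 (3 of 50) once the separate specificities are known. The larger omission is the number of EOS infants missed by CBC and I/T ratio but caught by the markers, which can be bounded but is not reported. The illustrative counts rest on the section 2 and 2.2 figures applying to this cohort and on an assumed EOS rate; the absence of a paired comparison depends on neither. Aim 1 is unaffected and the data remain usable. This is a worthwhile and inexpensive improvement, for estimation only.

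**What to change.** In section 3 (Aim 2) and section 14, add a descriptive within-infant cross-tabulation, among infants with both sets of results, of CBC plus I/T ratio against the same tests with IL-6/CRP.

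- Fix the positivity and combination rules before results are examined. A cut-off chosen by ROC in the same data does not meet this. The rules are analysis definitions, not proposals for care.
- State the EOS definition and the specimen used for each test. Leave blood culture out of the comparator, and say why.
- Report, as paired counts with exact intervals: EOS infants newly caught, non-EOS infants newly flagged, and non-EOS infants un-flagged if both are required.
- Base the conclusion on the role of adding the markers on these counts, as estimation and not as a test.

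The cost is wording and one table, with no added blood or recruitment. There are two drawbacks. The EOS counts will be small and imprecise. Infants without enough serum will also drop out, because marker serum comes from the remainder of the cord sample (section 5) or left-over CBC blood (section 4), with no minimum volume guaranteed; the number lost should be reported.
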